8.1 Disease Parameters

Measurable disease: Measurable lesions are defined as those that can be accurately measured in at least one dimension (longest diameter in the plane of measurement is to be recorded) with a minimum size of:

- 10 mm by CT scan (or MRI) for studies with a slice thickness of ≤ 5 mm, or twice the slice thickness
- 10 mm caliper measurement by clinical exam (lesions which cannot be accurately measured with calipers should be recorded as non-measurable)
- 20 mm by chest X-ray (if clearly defined and surrounded by aerated lung)

All tumor measurements must be recorded in millimeters (or decimal fractions of centimeters).

Malignant lymph nodes: To be considered pathologically enlarged and measurable, a lymph node must be ≥ 15 mm in short axis when assessed by CT scan (CT scan slice thickness recommended to be no greater than 5 mm). At baseline and in follow-up, only the short axis will be measured and followed.

Note: Tumor lesions that are situated in a previously irradiated area will only be considered measurable, if they have had subsequent progression by at least 5 mm.

Non-measurable disease: All other lesions (or sites of disease), including small lesions (longest diameter < 20 mm with conventional techniques or < 10 mm using CT scan), are considered non-measurable disease. Bone lesions, leptomeningeal disease, ascites, pleural/pericardial effusions, lymphangitis cutis/pulmonis, inflammatory breast disease, abdominal masses (not followed by CT or MRI), and cystic lesions are all non-measurable.

Target lesions: All measurable lesions up to a maximum of 2 lesions per organ and 5 lesions in total should be identified as **target lesions** and recorded and measured at baseline. Target lesions should be selected on the basis of their size (lesions with the longest diameter), representative of all involved organs, and those that lend themselves to reproducible repeated measurements. If a non-nodal lesion is either not present or is initially measured with longest diameter <10mm as a non-target then grows to ≥ 10 mm after baseline, this lesion then becomes a new target lesion as per irRECIST criteria. The non-nodal longest diameter is then added to the sum of diameters, and patient response is calculated with the new lesion.

Lymph nodes merit special mention since they are normal anatomical structures which may be visible by imaging even if not involved by tumor. Pathological nodes which are defined as measurable and may be identified as target lesions must meet the criterion of a short axis of ≥ 15 mm by CT scan. Only the short axis of these nodes will contribute to the baseline sum. The short axis of the node is the diameter normally used by radiologists to judge if a node is involved by solid tumor. Nodal size is normally reported as two dimensions in the plane in which the image is obtained (for CT scan this is almost always the axial plane; for MRI the plane of acquisition may be axial, sagittal or coronal). The smaller of these measures is the short axis. For example, an abdominal node which is reported as being 20 mm x 30 mm has a short axis of 20 mm and qualifies as a malignant, measurable node. In this example, 20 mm should be recorded as the node measurement. All other pathological nodes (those with short axis ≥ 10 mm but <15 mm) should be considered non-target lesions. Nodes that have a short axis <10 mm are considered nonpathological and should not be recorded or followed.

A sum of the diameters (longest for non-nodal lesions, short axis for nodal lesions) for all target lesions will be calculated and reported as the baseline sum diameters. If lymph nodes are to be included in the sum, then as noted above, only the short axis is added into the sum. The baseline sum diameters will be used as reference to further characterize any objective tumor regression in the measurable dimension of the disease. If a non-target lymph node grows to >15mm after baseline, this node then becomes a new target lesion as per irRECIST. The nodal short axis is then added to the sum of diameters, and patient response is calculated with the new lesion.

Non-target lesions: All other lesions (or sites of disease) including pathological lymph nodes should be identified as non-target lesions and should also be recorded at baseline. Measurements are not required and these lesions should be followed as ‘present’, ‘absent’, or in rare cases ‘unequivocal progression’ (more details to follow). In addition, it is possible to record multiple non-target lesions involving the same organ as a single item on the case record form (e.g. ‘multiple enlarged pelvic lymph nodes’ or ‘multiple liver metastases’)

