3.2 Secondary Objectives

- (1) **Objective:** Determine the pre-treatment dexamethasone dose and duration needed to induce ORR to pembrolizumab of $\geq 33\%$ in patients whose NSCLC has progressed on 1st line immunotherapy.
- (2) **Objective:** Determine ORR to Pembrolizumab assessed by FDG-PET
- (3) **Objective:** Determine the relationship between sensitivity to dexamethasone using pre- and post- FLT PET scans and ORR (by FDG PET).
- (4) **Objective:** Determine the relationship between sensitivity to dexamethasone using pre- and post- FLT PET scans and GR expression by IHC.
- (5) **Objective:** Evaluate response based on immune-related RECIST (ir-RECIST) criteria and compare to response rate as evaluated by RECIST v1.

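### Section 8.1 adds the full diameter of a small lesion already present at baseline to the irRECIST follow-up sum, but not to the reference sum

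*Combined protocol and SAP*

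**What the plan says.** Section 8.1 (target lesions) applies one irRECIST rule to two situations: a non-nodal lesion that was absent at baseline, and one that was "initially measured with longest diameter <10mm as a non-target then grows to" 10 mm or more. In both, the lesion becomes a new target lesion and "The non-nodal longest diameter is then added to the sum of diameters, and patient response is calculated with the new lesion". The lymph-node paragraph has a parallel rule: "If a non-target lymph node grows to >15mm after baseline, this node then becomes a new target lesion as per irRECIST", with its short axis added to the sum.

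The reference is defined separately. In 8.1 the diameters "for all target lesions will be calculated and reported as the baseline sum diameters", and "The baseline sum diameters will be used as reference to further characterize any objective tumor regression in the measurable dimension of the disease". In 8.3, partial response (PR) is a fall of at least 30% from the baseline sum, and progressive disease (PD) is a rise of at least 20% from the smallest sum recorded. No sentence says what happens to either reference when a lesion that already existed is promoted.

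Three other provisions bear on this:

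- Section 8.0 describes irRECIST as adding measurements of new lesions only. It re-labels a first RECIST v1.1 PD as irSD and requires a confirming scan at 4 to 8 weeks before irPD.
- Section 8.1 (non-target lesions) does not require measurements. These lesions are followed qualitatively.
- Secondary objective 3.2(5) is: "Evaluate response based on immune-related RECIST (ir-RECIST) criteria and compare to response rate as evaluated by RECIST v1".

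**The concern.** For a lesion absent at baseline, adding its whole diameter is right, because its earlier contribution was zero. For a lesion on record at, say, 9 mm, the follow-up sum includes it in full while the reference counts it as zero. Numerator and denominator then cover different sets of lesions, and the change in the sum reflects the promotion more than any growth.

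What is at stake is the within-patient comparison of irRECIST and RECIST v1.1 response. Section 8.0 presents irRECIST as the reading that tolerates apparent early progression. Under the 8.1 rule it can be the stricter of the two on a 1 mm change, for reasons of arithmetic alone. Because non-target measurements are not required, the baseline size needed to correct this later may not be on file.

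**Working it through.** The plan gives no worked example for this rule, so there is no figure of its own to reproduce. The thresholds come from 8.1 and 8.3. The sums and the 9 to 10 mm lesion are illustrative assumptions. Small sums are permitted: 5.1 requires only one measurable lesion, and 8.1 sets the minimum size at 10 mm by CT.

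Notation: B = baseline target sum; R = smallest sum recorded; S = follow-up sum of the original targets; d = diameter of the promoted lesion at follow-up; d0 = its earlier diameter. All are in mm.

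**First-PD threshold, original targets unchanged (S = R)**

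- Rule as written: change = (R + d)/R − 1 = d/R. With d = 10, this is 20% or more when R ≤ 10/0.20 = 50.
- Like-for-like: change = (R + d)/(R + d0) − 1, with d0 = 9.

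| R | As written | Like-for-like |
|---|---|---|
| 10 | +100% | 20/19: +5.3% |
| 40 | 50/40: +25% | 50/49: +2.0% |
| 50 | 60/50: +20% | 60/59: +1.7% |
| 51 | 61/51: +19.6% | 61/60: +1.7% |
| 100 | 110/100: +10% | 110/109: +0.9% |

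For a node going from 14.5 to 15.5 mm, the threshold is met when R ≤ 15.5/0.20 = 77.5.

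**Partial response, B = 50, lesion 9 to 10 mm**

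- RECIST v1.1 as in 8.3, lesion left as non-target: PR if S ≤ 0.70 × 50 = 35.
- Rule as written: PR if S + 10 ≤ 35, so S ≤ 25.
- Like-for-like: PR if S + 10 ≤ 0.70 × 59 = 41.3, so S ≤ 31.3.

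This splits the range as follows:

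- S ≤ 25: PR under all three.
- 25 < S ≤ 31.3: PR is lost only because the reference omits the 9 mm. At S = 30, the rule gives 40/50 = −20% (SD), like-for-like gives 40/59 = −32% (PR), and RECIST v1.1 gives 30/50 = −40% (PR).
- 31.3 < S ≤ 35: PR is lost under irRECIST even with a matched reference. At S = 35, the rule gives 45/50 = −10% and like-for-like gives 45/59 = −23.7%.

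The RECIST v1.1 PR is normally kept because the 8.3 table gives PR when targets are in PR, non-targets are not in PD and there are no new lesions. A 1 mm change in a non-target lesion would not ordinarily be unequivocal progression.

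**Weight of one patient.** Section 11.1 has 21 patients at the selected duration if the third stage is reached. One reclassified responder moves a response rate by 1/21 = 4.8 percentage points.

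**The case against.** The best defence has five parts.

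- *The omission is inferred.* No sentence says the reference stays unadjusted, and 8.1 speaks of the lesion as having been measured initially, so a baseline diameter may exist. That is fair. But the baseline sum is defined on target lesions only, no restatement rule is given, and non-target measurements are not required. A reader following the text would leave the reference alone.
- *Progression must be confirmed.* A reader might infer that the rule yields unconfirmed, false irRECIST progressions. The documents do not support this: 8.0 makes a first PD irSD until a confirming scan. What stands is narrower. Section 8.0 could be read as confirming irPD when the sum simply stays raised, while 8.3 (treatment beyond progression) asks for a further 20% and at least 5 mm from the initial PD, which a lesion staying at 10 mm would not meet. Those two sections must be reconciled.
- *Stable targets do not affect response rates.* SD and PD are both non-responses, so the +25% case leaves both rates unchanged. This stands. Only the PR calculation bears on objective 3.2(5).
- *Not every lost PR comes from the asymmetry.* A reader might blame it for the whole gap between 30% shrinkage and what the rule demands. At a 50 mm baseline the rule demands 50%, but a matched reference already demands 37.4% (31.3/50). The first step, from 30% to 37.4%, comes from counting the lesion at all.
- *The consequence is limited.* Section 11 attaches no test or decision rule to the irRECIST comparison, and the powered ORR test in 11.1 and 11.5 uses the 12-week FDG PET. Best overall response is the best recorded before progression, so a later promotion does not erase a PR already recorded. All of this stands, and it limits the weight of the point.

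**Conclusion.** The point holds as a defect in the irRECIST measurement rule. A lesion present at baseline enters the follow-up sum in full and the reference not at all, so 1 mm of change counts as at least 10 mm. One promoted 10 mm lesion reaches the first-PD size at reference sums up to 50 mm. At a 50 mm baseline, the asymmetry alone costs a PR across a 6.3 mm band of target shrinkage (31.3 − 25). Objective 3.2(5) would then partly compare bookkeeping rather than criteria.

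This rests on reading 8.1 as leaving the reference sums unadjusted, and on an assumed 9 mm earlier diameter. It also takes the promoted lesion as entering through the sum, as 8.1 directs. If it were instead treated as a new lesion under 8.3, PR would be barred at any sum size.

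A reader might want to put a rate on misclassification from measurement error near the threshold. The documents give neither the number of near-threshold lesions nor the reading error, so no such rate can be derived. The FLT-PET primary endpoint is not affected. The change should be made, but it does not threaten the trial's main conclusion.

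**What to change.** State in 8.1 that when a lesion present at baseline is promoted, its baseline and interim diameters are measured on the existing images and added to the baseline and nadir reference sums. In the examples above, the stable case then never exceeds +5.3%, and the PR at S = 30 is kept.

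Alternatively, align 8.1 with 8.0 and with its own non-target paragraph: add only lesions absent at baseline, and keep recorded non-targets in the qualitative assessment. The stable case is then 0%, and the PR is kept at both S = 30 and S = 35. The two options differ for targets between 31.3 and 35 mm at a 50 mm baseline, so the choice should be made before response is read.

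Apply the same wording to the nodal rule. Separately, reconcile 8.0 and 8.3 on whether a persistently raised sum confirms irPD.

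Cost: a few sentences. The first option also needs a few extra measurements on scans already taken. Neither needs new imaging.

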8.2 Guidelines for Evaluation of Measurable Disease

All measurements should be recorded in metric notation, using calipers if clinically assessed. All baseline evaluations should be performed as close as possible to the treatment start and never more than 4 weeks before enrollment.

The same method of assessment and the same technique should be used to characterize each identified and reported lesion at baseline and during follow-up. Imaging based evaluation

should always be done rather than clinical examination unless the lesion(s) being followed cannot be imaged but are assessable by clinical exam.

Clinical lesions: Clinical lesions will only be considered measurable when they are superficial and > 10 mm diameter as assessed using calipers (e.g. skin nodules). For the case of skin lesions, documentation by color photography including a ruler to estimate the size of the lesion is suggested. As noted above, when lesions can be evaluated by both clinical exam and imaging, imaging evaluation should be undertaken since it is more objective and may also be reviewed at the end of the study.

CT and MRI: CT is the best currently available and reproducible method to measure lesions selected for response assessment. This guideline has defined measurability of lesions on CT scan based on the assumption that CT slice thickness is 5 mm or less. When CT scans have slice thickness greater than 5 mm, the minimum size for a measurable lesion should be twice the slice thickness. MRI is also acceptable in certain situations (e.g. for body scans).

Ultrasound: Ultrasound is not useful in assessment of lesion size and should not be used as a method of measurement. Ultrasound examinations cannot be reproduced in their entirety for independent review at a later date and, because they are operator dependent, it cannot be guaranteed that the same technique and measurements will be taken from one assessment to the next. If new lesions are identified by ultrasound in the course of the study, confirmation by CT or MRI is advised. If there is concern about radiation exposure at CT, MRI may be used instead of CT in selected instances.

8.3 Response Criteria

Evaluation of Target Lesions

Complete Response (CR): Disappearance of all target lesions, determined by two separate observations conducted not less than 4 weeks apart. There can be no appearance of new lesions.

Partial Response (PR): At least a 30% decrease in the sum of the longest diameter (LD) of target lesions, taking as reference the baseline sum LD. There can be no appearance of new lesions.

Progressive Disease (PD): At least a 20% increase in the sum of the LD of target lesions, taking as reference the smallest sum LD recorded since the treatment started, or the appearance of one or more new lesions.

Stable Disease (SD): Neither sufficient shrinkage to qualify for PR nor sufficient increase to qualify for PD, taking as reference the smallest sum LD since the treatment started.

Evaluation of Non-Target Lesions

Complete Response (CR): Disappearance of all non-target lesions and normalization of tumor marker level.

Incomplete Response/Stable Disease (SD): Persistence of one or more non-target lesion(s) and/or maintenance of tumor marker level above the normal limits.

Progressive Disease (PD): Appearance of one or more new lesions and/or unequivocal progression of existing non-target lesions.

Evaluation of Best Overall Response

The best overall response is the best response recorded from the start of the treatment until disease progression/recurrence (taking as reference for progressive disease the smallest measurements recorded since the treatment started). The patient's best response assignment will depend on the achievement of both measurement and confirmation criteria.

Target Lesions	Non-Target Lesions	New Lesions	Overall Response	Best Response for this Category Also Requires:
CR	CR	No	CR	≥4 wks. confirmation
CR	Non-CR/SD	No	PR	≥4 wks. confirmation
PR	Non-PD	No	PR	
SD	Non-PD	No	SD	Documented at least once ≥4 wks. from baseline
PD	Any	Yes or No	PD	no prior SD, PR or CR
Any	PD*	Yes or No	PD	
Any	Any	Yes	PD	

* In exceptional circumstances, unequivocal progression in non-target lesions may be accepted as disease progression.
 
Note: Patients with a global deterioration of health status requiring discontinuation of treatment without objective evidence of disease progression at that time should be reported as “symptomatic deterioration”. Every effort should be made to document the objective progression even after discontinuation of treatment.
				

Treatment Beyond Progression

Accumulating evidence indicates a minority of subjects treated with immunotherapy may derive clinical benefit despite initial evidence of PD.

Subjects will be permitted to continue study treatment beyond initial RECISTv1.1 defined PD, assessed by the investigator, as long as they meet the following criteria:

- Investigator determined clinical benefit
- Tolerance of study drug
- Stable performance status
- Treatment beyond progression will not delay an imminent intervention to prevent serious complications of disease progression (e.g., CNS metastases)
- Tumor markers are stable/improving, if expressed

A radiographic assessment/ scan should be performed within 4-8 weeks of initial investigator-assessed progression to determine whether there has been a decrease in the tumor size or continued PD (termed irPD). The assessment of clinical benefit should be balanced by clinical judgment as to whether the subject is clinically deteriorating and unlikely to receive any benefit from continued treatment.

If the investigator feels that the subject continues to achieve clinical benefit by continuing treatment, the subject should remain on the trial and continue to receive monitoring according to the Study Calendar (see Table 7.2).

For the subjects who continue study therapy beyond progression, further progression is defined as an additional 20% increase in tumor burden with a minimum 5 mm absolute increase from time of initial PD. This includes an increase in the sum of diameters of all target lesions and/or the diameters of new measurable lesions compared to the time of initial PD. Study treatment should be discontinued permanently upon documentation of further progression (i.e. irPD).

Duration of Response

Duration of overall response: The duration of overall response is measured from the time measurement criteria are met for CR or PR (whichever is first recorded) until the first date that recurrent or progressive disease is objectively documented (taking as reference for progressive disease the smallest measurements recorded since the treatment started).

The duration of overall CR is measured from the time measurement criteria are first met for CR until the first date that recurrent disease is objectively documented.

Duration of stable disease: Stable disease is measured from the start of the treatment until the criteria for progression are met, taking as reference the smallest measurements recorded since the treatment started.

Progression-Free Survival

Progression-free survival is defined as the duration of time from start of treatment to time of progression.

9.0 ADVERSE EVENTS

Adverse event monitoring and reporting is a routine part of every clinical trial and is done to ensure the safety of subjects enrolled in the studies as well as those who will enroll in future studies using similar agents. Data on adverse events will be collected from the time of the initial dose of dexamethasone through 30 days after the last dose of pembrolizumab (whichever is later). Serious adverse events will be collected from the time of the initial dose of dexamethasone through 30 days after the last dose pembrolizumab (whichever is later). Any serious adverse event that occurs more than 30 days after the last dose of pembrolizumab and is considered related to the study must also be reported. Serious Adverse Events (SAEs) will continue to be followed until:

- Resolution or the symptoms or signs that constitute the serious adverse event return to baseline;
- There is satisfactory explanation other than the study drugs for the changes observed;
- The patient is lost to follow-up or withdraws consent; or
- Death.

The investigator is responsible for the detection, documentation, grading and assignment of attribution of events meeting the criteria and definition of an AE or SAE. The definitions of AEs and SAEs are given below. It is the responsibility of the principal investigator to ensure that all staff involved in the trial is familiar with the content of this section.

Any medical condition or laboratory abnormality with an onset date before enrollment onto study is considered to be pre-existing in nature. Any known pre-existing conditions that are ongoing at time of study entry should be considered medical history.

All events meeting the criteria and definition of an AE or SAE, as defined in Section 9.1, occurring from the initial dose of dexamethasone through 30 days following the last dose of pembrolizumab must be recorded as an adverse event regardless of frequency, severity (grade) or assessed relationship to the study drugs.

In addition to new events, any increase in the frequency or severity (i.e., toxicity grade) of a pre-existing condition that occurs after the patient begins study is also considered an adverse event.

Adverse events will not be collected for subjects during the pre-screening period (for determination of archival tissue status) as long as that subject has not undergone any protocol-specified procedure or intervention. If the subject requires a blood draw, fresh tumor biopsy etc., the subject is first required to provide consent to the main study and AEs will be captured according to guidelines for standard AE reporting.

Investigators are not obligated to actively seek AE or SAE or other reportable safety events in former study participants. However, if the investigator learns of any SAE, including a

death, at any time after a participant has been discharged from the study, and he/she considers the event to be reasonably related to the study treatment or study participation, the investigator must promptly notify the IRB.

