At the end of treatment, all patients will continue to be followed for a minimum of 30 days for AE monitoring. Subjects will have post-treatment follow-up for disease status, including initiation of non-study cancer therapy until death, withdrawal of consent, or becoming lost to follow-up.

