7.2 Treatment Calendar

SCHEDULE OF EVENTS COHORT 1

Procedure	Screening (within 28 days prior to Day 0) ¹	Baseline Day 0	(C1D1)	Lead In C2 and C3	(C2 and 3D1) (± 3Days)	(C4+) (± 3 Days)	EOT	Follow Up ¹
Informed Consent	X							
Medical History	X							
Physical exam	X		X		X	X	X	
Vital Signs	X		X		X	X	X	
ECOG performance status	X		X		X	X	X	
Adverse Events	X		X		X	X	X	X
Concomitant Medications	X		X		X	X	X	X
CBCPD	X		X		X	X	X	
Comp	X		X		X	X	X	
Coagulation (PT/aPTT) ⁷	X							
FDG PET/CT-Chest (VA Ann Arbor) ²	X					X	X	
CT Abdomen/Pelvis ³	X							
Research Blood ⁴		X	X		X			
FLT PET (University of Michigan)		X	X					
Dexamethasone ⁵		X		X	X			
Pembrolizumab ⁶			X		X	X		

¹ Follow Up: Phone call 6 weeks after EOT including any new treatments

² FDG PET/CT-Chest: C4D1 (±7days), then Every 12 weeks (±7days)

³ CT-Abdomen/Pelvis: at screening, C4D1 (±7days), then Every 12 weeks (±7days) **only if disease is present in that area**

⁴ Research Blood: T/TK, SAP, cytokines, chemokines, immune cell subsets; Drawn with 1st FLT PET, 2nd FLT PET, C1D1, C2D1, C3D1 only

⁵ Dexamethasone given orally. Start immediately after FLT PET Day 0 – Day 9. Lead in Day 9-17

⁶ Pembrolizumab given up to 1 year every 21 days

⁷ Only required if clinically indicated or on anticoagulants

SCHEDULE OF EVENTS COHORT 2

Procedure	Screening (within 28 days prior to Day 0) ¹	Baseline Day 0	(C1D1)	Lead In C2 and C3	(C2 and 3D1) (± 3Days)	(C4+) (± 3 Days)	EOT	Follow Up ¹
Informed Consent	X							
Medical History	X							
Physical exam	X		X		X	X	X	
Vital Signs	X		X		X	X	X	
ECOG performance status	X		X		X	X	X	
Adverse Events	X		X		X	X	X	X
Concomitant Medications	X		X		X	X	X	X
CBCPD	X		X		X	X	X	
Comp	X		X		X	X	X	
Coagulation (PT/aPTT) ⁷	X							
FDG PET/CT-Chest (VA Ann Arbor) ²	X					X	X	
CT Abdomen/Pelvis ³	X							
Research Blood ⁴		X	X		X			
FLT PET (University of Michigan)		X	X					
Dexamethasone ⁵		X		X	X			
Pembrolizumab ⁶			X		X	X		

¹ Follow Up: Phone call 6 weeks after EOT including any new treatments

² FDG PET/CT-Chest: C4D1 (±7days), then Every 12 weeks (±7days)

³ CT-Abdomen/Pelvis: at screening, C4D1 (±7days), then Every 12 weeks (±7days) **only if disease is present in that area**

⁴Research Blood: T/TK, SAP, cytokines, chemokines, immune cell subsets; Drawn with 1st FLT PET, 2nd FLT PET, C1D1, C2D1, C3D1 only

⁵ Dexamethasone given orally. Start immediately after FLT PET Day 0 – Day 9. Lead in Day 9-17

⁶Pembrolizumab given up to 1 year every 21 days

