7.3 Management of Adverse Events

AEs associated with pembrolizumab exposure may represent an immunologic etiology. These immune-related AEs (irAEs) may occur shortly after the first dose or several months after the last dose of pembrolizumab treatment and may affect more than one body system simultaneously. Therefore, early recognition and initiation of treatment is critical to reduce complications. Based on existing clinical trial data, most irAEs were reversible and could be managed with interruptions of pembrolizumab, administration of corticosteroids and/or other supportive care. For suspected irAEs, ensure adequate evaluation to confirm etiology or exclude other causes. Additional procedures or tests such as bronchoscopy, endoscopy, skin biopsy may be included as part of the evaluation. Based on the severity of irAEs, withhold or permanently discontinue pembrolizumab and administer corticosteroids. Dose modification and toxicity management guidelines for irAEs associated with pembrolizumab are provided in **Table 4**.

Table 4: Dose modification and toxicity management guidelines for immune-related AEs associated with pembrolizumab

General instructions:				

 1. Corticosteroid taper should be initiated upon AE improving to Grade 1 or less and continue to taper over at least 4 weeks. 2. For situations where pembrolizumab has been withheld, pembrolizumab can be resumed after AE has been reduced to Grade 1 or 0 and corticosteroid has been tapered. Pembrolizumab should be permanently discontinued if AE does not resolve within 12 weeks of last dose or corticosteroids cannot be reduced to ≤ 10 mg prednisone or equivalent per day within 12 weeks. 3. For severe and life-threatening irAEs, IV corticosteroid should be initiated first followed by oral steroid. Other immunosuppressive treatment should be initiated if irAEs cannot be controlled by corticosteroids. 				
Immune-related AEs	Toxicity grade or conditions (CTCAEv4.0)	Action taken to pembrolizumab	irAE management with corticosteroid and/or other therapies	Monitor and follow-up

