7.5.1 End of Treatment Follow-up Visits

The mandatory Safety Follow-Up Visit should be conducted within 30 +/- 10 days after the last dose of pembrolizumab. Subjects with an AE of Grade >1 will be further followed until the resolution of the AE to Grade 0-1 or until beginning of a new antineoplastic therapy, whichever occurs first. Procedures should be conducted according to the Treatment Calendar in Section 7.2. SAEs that occur within 30 days of the end of treatment should be followed and recorded.

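### Section 9.0 closes adverse-event collection by the last pembrolizumab dose alone, in conflict with 2.1, 6.5, 7.5.1 and the calendars, so cover after a final dexamethasone course can be as short as 6 to 13 days

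*Combined protocol and SAP*

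**What the plan says.** Section 9.0 opens collection of both AEs and SAEs at the first dexamethasone dose and ends it at one date: "initial dose of dexamethasone through 30 days after the last dose of pembrolizumab (whichever is later"). The recording rule further down 9.0 repeats the pembrolizumab anchor without the later-of phrase: events "occurring from the initial dose of dexamethasone through 30 days following the last dose of pembrolizumab must be recorded as an adverse event".

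Section 7.5.1 ties the visit to the same drug: "The mandatory Safety Follow-Up Visit should be conducted within 30 +/- 10 days after the last dose of pembrolizumab". The same paragraph, however, counts SAEs for 30 days from the end of treatment. Section 2.1 also uses the end of treatment, after which "all patients will continue to be followed for a minimum of 30 days for AE monitoring", and 6.5 gives 30 days from the same point. None of these sections says which drug's last dose is the end of treatment.

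The calendars in 7.2 mark the Adverse Events row in the follow-up column for all three cohorts. Footnote 1 defines that column: "Follow Up: Phone call 6 weeks after EOT including any new treatments".

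On late events, 7.3 states: "These immune-related AEs (irAEs) may occur shortly after the first dose or several months after the last dose of pembrolizumab treatment". Section 9.0 keeps one late category reportable: "Any serious adverse event that occurs more than 30 days after the last dose of pembrolizumab and is considered related to the study". It adds: "Investigators are not obligated to actively seek AE or SAE or other reportable safety events in former study participants".

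Dexamethasone is the first trial treatment (5.2 and 6.1.1), and the safety population in 11.3 takes in anyone who receives any protocol treatment.

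**The concern.** A rule that takes the later of two dates needs two dates, and 9.0 supplies one. The missing term appears to be the last dexamethasone dose. That matters here because dexamethasone is the component under test, comes before each of the first three infusions, and can be the last study drug a patient takes.

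Two groups fall through the text of 9.0. A patient who stops during the first course never has a pembrolizumab date, so neither the window nor the mandatory visit can be dated, although that patient is in the safety population. A patient who takes a further course and then misses the infusion has the window counted back to the earlier infusion.

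At stake is complete and uniform safety capture. The safety population, the monthly committee review in 13.4 and the adverse-reaction criterion for early termination in 6.6 all draw on these data, and 4.2.2 says there are no phase I data on this sequence. With several anchors in force, staff could apply different windows to similar patients.

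**Working it through.** No power or error-rate formula applies. The check is calendar arithmetic on the diaries in Appendix IV, followed by a comparison of the anchors.

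**Inputs**
- Course lengths (6.1.1 and the diaries): Cohort 1, 7 + 1 + 1 = 9 days; Cohort 2, 10 + 2 + 1 = 13 days; Cohort 3, 13 + 3 + 1 = 17 days.
- Wash-out: 3 days (6.1.1).
- Cycle: 21 days for Cohorts 1 and 2. For Cohort 3, 28 days in section 1.0 and its diary, but 21 days in Table 2 and its calendar.
- Window: 30 days after the last infusion (9.0).

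**Step 1: reproduce the diaries.** Last dexamethasone day = next infusion day − 3 − 1. First day = last day − course length + 1.
- Cohort 1: next infusion Day 22 gives Days 10–18; Day 43 gives Days 31–39.
- Cohort 2: Day 22 gives Days 6–18; Day 43 gives Days 27–39.
- Cohort 3: Day 29 gives Days 9–25; Day 57 gives Days 37–53.

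All six courses match the diaries.

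**Step 2: gap when the course is completed and the next infusion is missed.** Closing day = last infusion day + 30. Gap = closing day − last dexamethasone day. Cover gained by a 30-day count from the last dose of either drug = (last dexamethasone day + 30) − closing day.

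| Cohort | Last infusion | Closing day under 9.0 | Last dexamethasone day | Gap | Cover gained |
|---|---|---|---|---|---|
| 1 and 2 | Day 1 | 1 + 30 = 31 | 18 | 31 − 18 = 13 | 48 − 31 = 17 |
| 1 and 2 | Day 22 | 22 + 30 = 52 | 39 | 52 − 39 = 13 | 69 − 52 = 17 |
| 3 | Day 1 | 1 + 30 = 31 | 25 | 31 − 25 = 6 | 55 − 31 = 24 |
| 3 | Day 29 | 29 + 30 = 59 | 53 | 59 − 53 = 6 | 83 − 59 = 24 |

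The diaries show no dexamethasone after infusion 3, so the gap arises only after infusions 1 and 2.

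**Step 3: sensitivity.**
- Cohort 3 on a 21-day cycle: last dexamethasone day 22 − 3 − 1 = 18; gap 31 − 18 = 13 days.
- The lead-in in the calendar footnote ends on Day 17: gap 31 − 17 = 14 days.
- Shifting the course by the calendar's ±3 days: 10 to 16 days in Cohorts 1 and 2, 3 to 9 days in Cohort 3 on the 28-day cycle.
- A patient who stops in mid-course has a longer gap than those in the table.

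**Step 4: dexamethasone only.** There is no last infusion day, so the closing day in 9.0 and the 30 ± 10 day visit in 7.5.1 cannot be computed.

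**Step 5: the anchors side by side.** Last pembrolizumab dose: both sentences of 9.0 and the visit in 7.5.1. End of treatment, drug unspecified: 2.1, 6.5, the SAE sentence of 7.5.1, and the call in 7.2. If the end of treatment is taken as the last infusion, the call comes 42 − 30 = 12 days after the 9.0 window has closed. The calendar then asks for adverse events over a period in which 9.0 gives no routine instruction to record non-serious ones.

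**The case against.** The strongest reply is that the protocol as a whole does supply an end. A reader of 9.0 alone might infer that collection never closes for a dexamethasone-only patient. Sections 2.1 and 6.5 and the SAE sentence of 7.5.1 give 30 days from the end of treatment, and since dexamethasone counts as trial treatment they can be read to cover that patient. This stands against any claim that the protocol has no end date. It does not remove the conflict: the end of treatment is not defined by drug, 7.5.1 uses both anchors in one paragraph, and 6.5 sends SAE collection back to 9.0.

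A reader might also infer that only related SAEs are captured after day 30. The calendars do not support that, because adverse events are marked at the six-week call. Section 7.5.1 also follows AEs above Grade 1 until they resolve to Grade 0–1 or a new therapy starts. The sentence on not actively seeking events concerns former participants, not everyone past day 30.

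Nor do the documents support saying that a tolerability conclusion would be biased. They state no safety or tolerability objective and plan no safety analysis beyond a population definition. Toxicity that makes a patient stop dexamethasone will usually arise on treatment, after the window has opened. Section 6.3 does not say that pembrolizumab is then withheld.

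The scenario is narrow, and the 6-day figure depends on which cycle length applies to Cohort 3. Both points stand. A visit permitted at day 20 is not itself a fault, since a visit window does not close event collection.

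**Conclusion.** The point holds as a conflict of anchors with a missing term in 9.0. Followed as written, 9.0 cuts collection to 13 days after the last dexamethasone dose in Cohorts 1 and 2, and to 6 days in Cohort 3 on the diary cycle (13 on the 21-day cycle). These figures assume a course completed on the diary days after infusion 1 or 2 and no further infusion. For a dexamethasone-only patient, 9.0 gives no closing date and 7.5.1 gives no visit date.

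The number affected is not given. A reader might take the drop-out allowance in 11.2 (39 − 31 = 8) as an estimate, but it covers drop-out of every kind and does not show how many patients stop between dexamethasone and infusion.

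On late immune events, the supported point is limited: 9.0 and the calendar disagree on whether non-serious events elicited at the six-week call are recorded, and 7.3 expects such events after the 30-day window. Extending collection through the 2-year survival record review would be a design preference with added work, and is not part of this point.

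**What to change.** 1. In 9.0 (both the collection and the recording sentences) and in 7.5.1, count the AE/SAE window and the safety visit from the later of the last dexamethasone dose and the last pembrolizumab dose.
2. Define the end of treatment the same way in 2.1 and 6.5, and use that definition for the SAE sentence of 7.5.1 and the end-of-treatment contacts in 7.2.
3. Reconcile 9.0 with the calendars by stating that AEs elicited at the existing six-week call, immune-related events included, are recorded.
4. Reconcile the Cohort 3 cycle length across section 1.0, Table 2, the calendar and the diary, because the size of the gap depends on it.

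For a patient whose last study drug is a completed dexamethasone course, the first change adds 17 days of cover in Cohorts 1 and 2 and 24 days in Cohort 3 on the diary cycle (17 if the 21-day cycle applies). A dexamethasone-only patient gains a defined end, 30 days after the last dose, and a datable visit. The cost is wording in five sections and a few more events to enter. The call already exists and the safety visit is already mandatory, so no new type of contact is needed. No dose or treatment rule changes.
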